1. BACKGROUND

The MEB, as the Reference Member State (RMS) for SEROQUEL and SEROQUEL XR, requested AstraZeneca to update the education materials in scope of the EU Risk Management Plan (RMP) and Summary of Product Characteristics (SmPC) changes with respect to hyperglycaemia and metabolic monitoring. The content and the messages for these educational materials have been agreed and distribution in the individual member states is ongoing.

AstraZeneca was also requested to provide a plan for assessing the effectiveness of these educational materials. During discussion with the MEB, it was communicated that there are 2 components to the assessment of effectiveness: process indicators (receipt and understanding of materials) and outcome indicators (changes in behaviour and effect on patients). To realize these 2 indicators, AstraZeneca is proposing 2 components for the evaluation of the effectiveness of the metabolic education: an objective, easy to understand and complete healthcare provider survey and the use of an Electronic Medical Records approach, as a potential means to assess the monitoring of patients.

This protocol describes the evaluation of the effectiveness of the distribution of metabolic educational materials sent to healthcare providers in the EU. It will be conducted via an evaluation survey that uses a questionnaire to assess the receipt of the educational material, whether the material was read, and to assess healthcare provider behaviour regarding the conduct of monitoring of metabolic parameters for patients treated with SEROQUEL and SEROQUEL XR. The survey will be conducted among healthcare providers who were targeted to receive the educational materials following local guidance and directives.

A companion proposal describes the evaluation of electronic medical record (EMR) data including details on objectives, the source of data, and the target healthcare provider-base for the database assessment.

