2. OBJECTIVES OF THE EVALUATION SURVEY

The healthcare provider survey is a questionnaire that will document the receipt of educational materials and assess the behaviour of healthcare providers around the following key metabolic monitoring messages communicated through the educational materials.

The key messages communicated in the educational materials are presented below.

Information on weight and hyperglycaemia has been updated in the "Special Warnings and Precautions" section of the label:

Weight:

Weight gain has been reported in patients who have been treated with Seroquel® or Seroquel® XR, and should be monitored and managed as clinically appropriate as in accordance with utilised antipsychotic guidelines*.

Hyperglycaemia:

Hyperglycaemia and/or development or exacerbation of diabetes mellitus occasionally associated with ketoacidosis or coma has been reported rarely, including some fatal cases (see section 4.8). In some cases, a prior increase in body weight has been reported which may be a predisposing factor. Appropriate clinical monitoring is advisable in accordance with utilised antipsychotic guidelines. Patients treated with any antipsychotic agent including Seroquel® or Seroquel® XR, should be observed for signs and symptoms of hyperglycaemia, (such as polydipsia, polyuria, polyphagia and weakness) and patients with diabetes mellitus or with risk factors for diabetes mellitus should be monitored regularly for worsening of glucose control. Weight should be monitored regularly.

Existing information on other metabolic parameters include the following:

Lipids:

Increases in triglycerides, LDL and total cholesterol, and decreases in HDL cholesterol have been observed in clinical trials with Seroquel® or Seroquel® XR. Lipid changes should be managed as clinically appropriate.

Metabolic Risk

Given the observed changes in weight, blood glucose (see hyperglycaemia) and lipids seen in clinical studies, there may be possible worsening of the metabolic risk profile in individual patients, which should be managed as clinically appropriate.

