3.1.1 Questions Regarding Key Monitoring Behavior

Question 1:

What is your medical specialty*? Please select one from the drop-down list below.

- O General Medicine/General Practice
- O Neurology
- O Psychiatry
- O Other SPECIFY:

* NOTE – OTHER SPECIALTIES TO BE INCLUDED BASED ON AUDIENCES TO WHOM MATERIAL WAS SENT

Question 2

Please think about your patients with schizophrenia, bipolar disorder, and/or major depressive disorder who are treated with Seroquel® or Seroquel® XR. Describe the "monitoring" of metabolic factors^{*} potentially related to treatment with Seroquel® or Seroquel® XR.

A. What proportions of your patients are being monitored by you, someone else in your practice or are referred to other healthcare providers? _____%

B. What proportion of your patients is referred to other healthcare providers for monitoring?

*Monitoring of metabolic factors includes: weight at initiation and during continuing treatment, ordering or reviewing lipid panel tests, observing patients for signs or symptoms associated with hyperglycaemia, ordering or reviewing tests for blood glucose measurement for patients with diabetes mellitus or in patients with risk factors for diabetes mellitus for worsening of glycaemic control, and counseling on nutrition, exercise and maintaining a healthy lifestyle

Question 3

Thinking now of the patients that you (or someone in your practice) monitor for metabolic issues potentially related to treatment with Seroquel® or Seroquel® XR, which of the following activities do you do? Please check all that apply.

- [□] I counsel patients taking Seroquel® or Seroquel® XR on healthy eating, exercise, and healthy lifestyle improvements
- ^D I monitor patients' weight at the initiation of treatment with Seroquel® or Seroquel® XR
- ^a I monitor patients' weight on a regular basis after initiating treatment with Seroquel® or Seroquel® XR
- I monitor tests for hyperlipidemia in patients who are taking Seroquel or Seroquel® XR
- [□] I observe for signs and symptoms of hyperglycaemia in patients who are taking Seroquel® or Seroquel® XR
- I monitor patients with diabetes mellitus or with risk factors for diabetes mellitus for worsening of glucose control if they are taking Seroquel® or Seroquel® XR

Question 4

The following question has two parts; please respond to both parts of the question.

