Appendix B Questionnaire

QUESTIONNAIRE

The questionnaire is designed to be administered as an on-line survey via Internet. The following are mock-up version of what the successive screens that would be displayed

Screen 3 Question 1:

What is your medical specialty*? Please select one from the drop-down list below.

- O General Medicine/General Practice
- O Neurology
- O Psychiatry
- O Other SPECIFY:

* NOTE – OTHER SPECIALTIES TO BE INCLUDED BASED ON AUDIENCES TO WHOM MATERIAL WAS SENT

Screen 4 Question 2:

Instructions: Please think about your patients with schizophrenia, bipolar disorder, and/or major depressive disorder who are treated with Seroquel® or Seroquel® XR. Describe the "monitoring" of metabolic factors^{*} potentially related to treatment with Seroquel® or Seroquel® XR.

- What proportions of your patients are being monitored by you, someone else in A. your practice or are referred to other healthcare providers? %
- What proportion of your patients is referred to other healthcare providers for B. monitoring? %

*Monitoring of metabolic factors includes: weight at initiation and during continuing treatment, ordering or reviewing lipid panel tests, observing patients for signs or symptoms associated with hyperglycaemia, ordering or reviewing tests for blood glucose measurement for patients with diabetes mellitus or in patients with risk factors for diabetes mellitus for worsening of glycaemic control, and counseling on nutrition, exercise and maintaining a healthy lifestyle

Screen 5 Question 3:

Instructions: Thinking now of the patients that you yourself monitor for metabolic issues potentially related to treatment with Seroquel® or Seroquel® XR, which of the following activities do you perform? Please check all that apply.

GEL Version ID: CNS.000-362-594.2.0 Approved Date Printed: 04-Jan-2013 Approved by [name] 21 Dec 2012 15:02:47

- ^a I counsel patients taking Seroquel® or Seroquel® XR on healthy eating, exercise, and healthy lifestyle improvements
- I monitor patients' weight at the initiation of treatment with Seroquel® or Seroquel® XR
 I monitor patients' weight on a regular basis after initiating treatment with Seroquel® or
- Seroquel® XR
- [□] I monitor tests for hyperlipidemia in patients who are taking Seroquel or Seroquel® XR
- I observe for signs and symptoms of hyperglycaemia in patients who are taking Seroquel® or Seroquel® XR

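### Question 2 counts lifestyle counselling as metabolic monitoring and sets no any-or-all rule, so the Question 2A percentage is a broadened, ambiguous measure of parameter monitoring

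*Protocol*

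**What the plan says.** Protocol Section 1 says that the questionnaire will "assess healthcare provider behaviour regarding the conduct of monitoring of metabolic parameters for patients treated with SEROQUEL and SEROQUEL XR". Section 2 sets the objective: to "assess the behaviour of healthcare providers around the following key metabolic monitoring messages communicated through the educational materials". The messages that follow cover weight, hyperglycaemia and glucose control, lipids, and overall metabolic risk. Some ask for monitoring, such as "Weight should be monitored regularly". Others add management or ask only for that. Weight "should be monitored and managed as clinically appropriate as in accordance with utilised antipsychotic guidelines", and on metabolic risk "there may be possible worsening of the metabolic risk profile in individual patients, which should be managed as clinically appropriate". The lipid message speaks of management only. Counselling is named in none of them.

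Section 3.1 says that the outcome measures are percentage estimates given by the physician. Question 2 is the only question that collects percentages. Part A asks for the share of patients monitored, whether by the respondent, within the practice or through referral. Part B asks for the share referred. A footnote defines monitoring for both parts. It lists weight, lipid tests, signs of hyperglycaemia and glucose tests in patients with diabetes or risk factors, and ends "for worsening of glycaemic control, and counseling on nutrition, exercise and maintaining a healthy lifestyle" in Section 3.1.1. Appendix B, Screen 4 has the same ending, "and counseling on nutrition, exercise and maintaining a healthy lifestyle". Neither place says how many of the listed activities a patient must receive in order to count.

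Question 3 gives counselling its own tick box beside separate boxes for the monitoring activities. Section 6 evaluates each behaviour individually, and its examples of combined behaviours are weight and hyperglycaemia/glucose.

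**The concern.** Every footnote item except counselling measures, tests or observes something. Counselling is an intervention and yields no reading of a parameter. Question 3 draws the same line: its counselling option is worded as counselling, and all its other options as monitoring or observing.

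Because 2A is a single number, the respondent mixes the two kinds of activity before any data reach the sponsor, and no later analysis can separate them. A provider who gives lifestyle advice but neither weighs nor tests could report those patients as monitored. A provider who measures everything but does not counsel could report fewer. Which error occurs depends on whether the respondent reads the list as any or as all, and the question does not say.

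At stake is the survey's one overall figure for how many patients are monitored. An upward error matters more, since it would make the risk-minimisation materials look better followed than they are.

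**Working it through.** **1. The texts side by side.**

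| Activity | Section 1 (parameters) | Section 2 messages | Question 2 footnote | Question 3 |
|---|---|---|---|---|
| Weight | fits | monitor and manage | yes | own ticks |
| Signs of hyperglycaemia | fits | observe | yes | own tick |
| Glucose control (diabetes or risk factors) | fits | monitor | yes | own tick |
| Lipids | fits | manage only | yes | own tick |
| Lifestyle counselling | measures no parameter | not named | yes | own tick, worded as counselling |

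Only counselling lies outside the Section 1 description and is also unnamed in Section 2.

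**2. Can Question 3 recover the information?** No. It records whether a provider does an activity, not in how many patients. It also covers only patients monitored by the provider or practice (in Appendix B, by the respondent alone), whereas 2A includes referred patients.

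**3. Is there a figure in the plan to test this against?** No. The only statistical figures are in Table 1 (Section 3.3), and these reproduce. At 61% with n = 100, 1.96 × √(0.61 × 0.39 / 100) = 0.0956, which gives 51.4% to 70.6% as printed. That interval is for 100 yes/no answers. 2A collects a percentage from each respondent, so the half-width of 9.6 points is not a yardstick for the bias.

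**4. Illustration under assumed inputs.** The protocol gives no rates. Let m be the true share of patients with parameters monitored, c the share of unmonitored patients who are counselled, and k the share of monitored patients who are also counselled.

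- If any activity suffices: 2A = m + (1 − m)c, so the error is +(1 − m)c.
- If all activities are needed: 2A = m × k, so the error is −m(1 − k).

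For m = 60%: 0.60 + 0.40 × 0.50 = 0.80, and 0.60 × 0.50 = 0.30. The grid is:

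| m | Any: c = 0 / 10 / 30 / 50% | All: k = 100 / 90 / 70 / 50% |
|---|---|---|
| 40% | 40 / 46 / 58 / 70% | 40 / 36 / 28 / 20% |
| 60% | 60 / 64 / 72 / 80% | 60 / 54 / 42 / 30% |
| 80% | 80 / 82 / 86 / 90% | 80 / 72 / 56 / 40% |

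The error vanishes when c = 0 on the first reading and when k = 100% on the second, that is, when counselling and parameter monitoring always occur together. A larger sample does not reduce it.

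**5. Does deleting counselling suffice?** No. It removes c and k, but m itself still depends on the reading. If any activity suffices, the share monitored is at least as large as the share for the most common remaining activity. If all are needed, it is at most the share for the least common one. The any-or-all rule is therefore a defect of its own.

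**The case against.** The strongest reply is that this is a deliberate definition and contradicts nothing. Section 1 describes the behaviour in a background sentence and does not define it. The only operational definition is the footnote, which is the same in the body and the appendix. Section 2 goes beyond measurement, and counselling could be a form of the management that it calls for. It also refers to antipsychotic guidelines that are not shown. If an item had to rest on a monitoring message, lipid tests would have to go as well. Question 3 and Section 6 report the parameter activities individually, free of counselling, and Section 1 mentions a companion evaluation of medical records. No success threshold is set, so no decision would flip. Every magnitude is assumed.

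Much of this stands. A reader might infer that 2A fails to measure the stated outcome, or that Section 1 formally excludes counselling. The documents support neither: every other footnote item matches a Section 2 topic, and Section 1 is only descriptive. The absence of a threshold and the assumed magnitudes are also fair points.

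Three things do not fall. Question 2 asks about monitoring, and management of a finding is a different act, which Question 3 itself words differently. Lipid tests can stay without inconsistency, because they measure a metabolic parameter, as Section 1 describes, and counselling does not. The individual reporting is a percentage of providers, so it cannot replace a share of patients, and the medical-records work is a separate proposal that does not repair this question.

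**Conclusion.** The point holds in a limited form. 2A is a broadened and ambiguous measure of parameter monitoring: its definition includes one activity that is not monitoring, and it states no any-or-all rule. The result may overstate or understate parameter monitoring. Neither size nor direction can be derived from the protocol. The ranges above rest wholly on assumed values of m, c and k, and the bias is zero if counselling always accompanies monitoring.

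It would be wrong to conclude that the survey leaves the monitoring messages unassessed, or that the reported rate is known to be inflated. The provider-level results from Question 3 are unaffected by this footnote. The point still deserves a change, because the fault lies in the wording shown to respondents and a statistical analysis plan could not correct it after fielding.

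**What to change.** 1. Delete the counselling clause from the Question 2 footnote in Section 3.1.1 and in Appendix B, Screen 4. Monitoring then means weight, lipid tests, signs and symptoms of hyperglycaemia, and glucose control.
2. State in the question whether a patient counts as monitored when any or when all of the remaining activities are done. If all, say how the glucose-test item is handled for patients to whom it does not apply, since the footnote limits it to those with diabetes or risk factors.
3. Keep counselling only as the separate Question 3 tick, and report it as a management activity.

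The cost is one clause removed and one sentence added. Section 4.1.2 places translation after validation, so the change is cheapest before the questionnaire is validated and should in any case precede translation. Once the survey has been fielded, the information cannot be recovered. The downside is that the 2A rate may come out lower, as it would if respondents had been counting patients who were only counselled.

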3.1 Study Design

This survey will be completed by a sample of healthcare providers who were targeted to receive the metabolic educational materials and either currently prescribe or have the potential to prescribe SEROQUEL or SEROQUEL XR. A sample of healthcare providers who were targeted for the educational materials will be approached to participate in the survey.

The survey will be administered using the following modality:

• Self-administered and Internet-based questionnaire accessed through a secure website instructing the participant to enter a unique code provided in the invitation.

The survey will begin with screening questions to confirm respondent eligibility to participate in the survey. Completion of the entire survey is expected to take less than 10 minutes.

The survey included in Appendix B is written to reflect the wording and screen-by-screen presentation of questions for an Internet-based survey administration.

All respondents who complete the survey and who provide their contact information will be mailed a fee consistent with approved market value for the physician's time for completing the survey.

The questions related to having received the educational materials and having read the information (measures of process) are closed-ended questions (answered affirmatively as yes/no/unsure response options). Questions related to physician behavior regarding monitoring of patients (measures of outcome) are percentage estimates provided by the physician.

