6. ANALYSIS

The survey questionnaire contains questions about the specialty of the physician sample completing the survey, questions specific to whether referrals are made to other healthcare providers for metabolic monitoring, whether the healthcare provider conducts monitoring of patients, general questions regarding receipt of the educational materials, and behavior about reading the materials. Information obtained from responses to each question of the survey will be reported as descriptive statistics. A frequency distribution of responses to each question (the number of respondents who give answers to each response option) will be presented.

Each risk minimization behavior will be evaluated individually.

Related behaviors, such as:

- Monitoring for weight
- Monitoring for signs and symptoms of hyperglycaemia and monitoring blood glucose changes in patients with diabetes mellitus will be combined to report the number of survey respondents who answered each risk minimization activity individually, any one activity and both activities. This will be expressed as a percent of the total number of respondents who answered the questions on these risk minimization activities.

Frequency distributions of the responses to having received SEROQUEL[®] / SEROQUEL[®] XR educational materials and behaviors about reading the educational materials, will also be calculated and displayed. The analysis of frequencies will include exact binomial 95% confidence intervals.

The following will be reported, as appropriate, as part of this analysis:

- The number of invitations issued to healthcare providers
- The number of healthcare providers screened for participation
- The number of healthcare providers eligible for participation
- The number of healthcare providers who completed the survey

- Description of healthcare provider survey participants, including:
 - Specialty of respondent
 - Country of practice
- Frequency distribution of responses to each survey question (the number of respondents who give each answer to each question)
- Percent of respondents selecting desired response to each question relating to each risk minimization activity and 95% confidence interval
- Percent of respondents demonstrating success of composite risk minimization activities and 95% confidence interval

Additional analyses may be performed as needed.

Risk Minimization Physician Survey Protocol

Drug Substance	Quetiapine fumarate
Study Code	D1443C000127
Edition Number	1

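### Question 3 asks about activities only among patients already monitored, as ticks with no 'none' option, so the Section 6 activity rates are not monitoring rates among treated patients

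*Protocol*

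**What the plan says.** **The base of Question 3.** Appendix B, Screen 5, begins "Thinking now of the patients that you yourself monitor for metabolic issues potentially related to treatment with" Seroquel or Seroquel XR. Section 3.1.1 has "Thinking now of the patients that you (or someone in your practice) monitor for metabolic issues potentially related to treatment with" the drug. Both leave out treated patients whom nobody in the practice monitors. They differ on patients monitored by a colleague.

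**The response format.** Appendix B continues "which of the following activities do you perform? Please check all that apply". Six activities follow: lifestyle counselling, weight at start, weight during treatment, lipid tests, signs and symptoms of hyperglycaemia, and glucose control in patients with diabetes or risk factors. Neither version prints an option for doing none of these or for monitoring nobody.

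**The stated type of measure.** Section 3.1: "Questions related to physician behavior regarding monitoring of patients (measures of outcome) are percentage estimates provided by the physician".

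**The preceding question.** Question 2A asks what percentage of the respondent's treated patients with the listed diagnoses are monitored, pooling the respondent, the practice and referral. Question 2B asks what percentage are referred out. A footnote begins "Monitoring of metabolic factors includes: weight at initiation and during continuing treatment, ordering or reviewing lipid panel tests" and goes on to name the remaining activities listed in Question 3.

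**The analysis.** Section 6 reports "Percent of respondents selecting desired response to each question relating to each risk minimization activity", and the percentage showing composite success, each with a 95% confidence interval. For the weight and hyperglycaemia groupings it counts each activity, any one and both, over the respondents who answered those questions.

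**The purpose.** Section 1 describes assessing provider behaviour in metabolic monitoring of patients treated with the drug. The key messages in Section 2 concern treated patients generally.

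**The concern.** Whether a provider follows a key message is a question about all the patients to whom the message applies. Question 3 first removes the treated patients who are not monitored and then asks what is done for the rest. A yes/no tick also discards how often an activity is done. A provider who monitors a handful of patients and one who monitors all of them can give identical answers, and Section 6 counts both as full successes.

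A second problem is the blank screen. Section 3.2.1 admits providers who only have the potential to prescribe, so some respondents may have no treated or no monitored patients. Without a 'none' option, a blank can mean that nothing is done or that the question was skipped. If blanks count as not answered, non-monitors leave the denominator.

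These rates are the only survey results tied to the separate messages on weight, hyperglycaemia, glucose and lipids. Section 3.3 treats performance of metabolic monitoring as the outcome measure and reads the lower confidence limit as a floor for the true level of effectiveness. That reading fails if the quantity being estimated is not monitoring of treated patients.

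**Working it through.** **1. The plan's own figures.** Table 1 follows from p ± 1.96·√(p(1−p)/100), with the lower limit cut at 0. For p = 51%: 1.96·√(0.51·0.49/100) = 9.8 points, giving 41.2% to 60.8% as printed. All 17 rows reproduce. The table describes sampling error only, so this point does not dispute it. It also means that the intervals cannot reveal an error in the base.

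**2. The bases side by side.**

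| Source | Patients in the base | Answer |
|---|---|---|
| Section 1 (purpose) | patients treated with the drug | – |
| Section 3.1 | not stated | percentage estimate |
| Question 2A | respondent's treated patients with the listed diagnoses | percentage, all activities pooled |
| Question 3, Section 3.1.1 | monitored by the respondent or the practice | six ticks |
| Question 3, Appendix B | monitored by the respondent personally | six ticks |

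No question combines the treated-patient base with a separate answer for each activity.

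**3. Loss of non-monitors (illustration; the documents give no values).** Let m be the share of 100 respondents who monitor any patient and a the share of those who tick an activity. Assume that non-monitors do none of the activities and leave the screen blank. If blanks are dropped, the reported rate is a. Over all respondents it is m·a.

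| a | m | Reported, blanks dropped | All respondents, m·a | Difference |
|---|---|---|---|---|
| 80% | 90% | 80% | 72% | 8 points |
| 80% | 70% | 80% | 56% | 24 points |
| 80% | 50% | 80% | 40% | 40 points |
| 60% | 50% | 60% | 30% | 30 points |

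If blanks are kept as zeros, this part of the difference disappears. For scale, the largest half-width in Table 1 is 9.8 points.

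**4. Ticks against treated patients (illustration).** Suppose respondents have equal caseloads, each monitors a share q of treated patients, and 80% tick the activity. The reported rate is 80% whatever q is. The share of treated patients covered is at most q × 80%: 16% for q = 20%, 40% for q = 50%, and 64% for q = 80%. It is a maximum because a tick need not mean that every monitored patient gets the activity. Handling blanks correctly does not remove this gap.

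**5. Whether Question 2 closes the gap.** For one provider, coverage for an activity is q·w, where w is the share of monitored patients who receive it. Question 2A minus 2B approximates the share monitored in the practice. Question 3 shows only whether the activity is done, not w. With q = 80%, w = 100% gives 80% coverage and w = 50% gives 40%, yet both providers answer Questions 2 and 3 identically. Under the Appendix B stem, 2A minus 2B does not even describe the same patients as Question 3, because it includes those monitored by colleagues.

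**The case against.** A reader might go further and infer that the activity rates are circular and driven towards 100%, because the Question 2 footnote defines monitoring by the same activities that Question 3 then offers. The documents do not support that. The footnote says what monitoring *includes*; it does not require every item. A provider who only weighs patients can truthfully tick the weight boxes alone, so Question 3 can still separate weight checks from lipid or glucose checks, and the rate can be well below 100%. The footnote's position also matters little, because Question 3 displays its own list. Moving the screen would withhold almost nothing.

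A dramatic example is possible. Half the providers monitor 10% of their patients, half monitor 90%, and all do every activity for those they monitor. Coverage is 0.5 × 10% + 0.5 × 90% = 50%, while Question 3 reports 100%. But the 100% is an assumption put into the example, and Question 2A would show a mean of 50% if answers were accurate and nobody was referred out.

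Three further points stand:
- The direction is not certain. Under the Appendix B stem a provider who delegates or refers all monitoring may tick nothing, which lowers the rate if that provider stays in the denominator. Several options speak of patients taking the drug, so some respondents may ignore the restriction in the stem.
- Section 2 frames the objective as provider behaviour, so a percentage of respondents is a legitimate summary. Section 3.3 sets no success threshold, so no rule turns a high rate into a finding that the materials work.
- Changing only the base and keeping the ticks would achieve little, since a provider monitoring 5% of patients could still tick.

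The companion medical-records evaluation in Section 1 is a separate proposal, described as a potential means of assessing monitoring. It does not change what this survey's rates mean. None of these points makes Question 3 a measure of monitoring among treated patients.

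**Conclusion.** The point holds as a mismatch between what Question 3 measures and how Sections 1, 3.1, 3.3 and 6 describe and use it. The per-activity and composite rates describe what respondents do for patients they already monitor. They cannot be read as monitoring rates among treated patients, and Question 2 cannot convert them because it is not split by activity.

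The likely direction is upward, for two reasons: low-coverage providers count fully, and non-monitors may leave the denominator. The size is unknown. The differences of 8 to 40 points, and the ceilings of 16% to 64% against a reported 80%, rest wholly on assumed values of m, a and q. The denominator effect further assumes that blanks are treated as not answered, which Section 6 leaves open. Separately, the two Question 3 stems contradict each other, and the tick format contradicts Section 3.1. Both are visible in the text without any assumption.

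**What to change.** Before validation and translation (Section 4.1):

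1. Use one stem in Section 3.1.1 and Appendix B, based on all the respondent's patients treated with Seroquel or Seroquel XR. For the glucose item, use those with diabetes or risk factors. State whether activities done by others in the practice count, and word the options to match, since they are now all in the first person.
2. For each of the six activities, ask for what percentage of these patients it is done (0 to 100%). This is the response type that Section 3.1 already states.
3. Add options for none or not monitoring, and for having no treated patients, so that a blank means only a missing answer.
4. In Section 6, make the denominator all eligible completers who have treated patients, with those who do not monitor counted as zero.
5. Report the mean or median percentage per activity with a confidence interval. Keep the individual, any-one and both counts by applying a cut-off fixed in advance, with the exact binomial intervals already planned.

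The cost is six short numeric entries in place of ticks, reliance on the respondent's recall of six percentages, a restated composite definition, and rates that may look less favourable. Table 1 would still describe the cut-off counts if 100 completers per country remain in the denominator, but not the means. If the ticks are kept instead, the report should at least say that the rates apply to monitored patients and show them beside Question 2.
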